6.0 AGENT FORMULATION AND PROCUREMENT

Formulation: Ruxolitinib (Jakafi®) is commercially available in the US in 5, 10, 15, 20, and 25 mg strength tablets. The tablet contains the active ingredient and may include the following commonly used excipients: microcrystalline cellulose, lactose, stearic acid, magnesium stearate, colloidal silicone dioxide, sodium starch glycolate, Povidone, and hydroxyl propyl cellulose. All excipients are of US and EuPh compendial grade.

The 5 mg (free base equivalent) and 25 mg (free base equivalent) tablets are packaged in HDPE bottles. All bottles of Incyte investigational product contain the following language: "Caution: New Drug-Limited by Federal Law to Investigational Use." The clinical supply for investigational use is the 5 mg tablet.

Storage and Stability: Ruxolitinib has been shown to be stable for up to 6 months at 40 degrees C and up to 24 months when stored at 25 degrees C.

Compatibility: Ruxolitinib may be taken either with food or without food

Handling: Qualified personnel, familiar with procedures that minimize undue exposure to themselves and the environment, should undertake the preparation, handling, and safe disposal of the chemotherapeutic agent in a self-contained and protective environment.

Availability: Ruxolitinib will be supplied free-of-charge by Incyte Corp.

7.0 CORRELATIVE/ SPECIAL STUDIES

Patients' plasma samples and peripheral blood cells will be obtained prior to and approximately 3 and 6 months of treatment, or as requested by PI for specific patients with unusual response or unusual clinical presentation.

Those samples will be stored at -20°C in the P.I.'s laboratory, using appropriate de-identifiers, and plasma cytokine levels (such as IL-1, IL-6, and IFNs (Verstovsek et al., 2008-0874) will be measured and changes in B-cell receptor signaling pathways will be assessed using standard technology.

8.0 PATIENT EVALUATION

Patients will be evaluated in accordance with our standard of care. Every clinic visit to MDACC will include a routine physical examination and standard laboratory tests including CBC with differential and, plts, chemistries to include creatinine and ALT, Immunoglobulin levels (IgG, IgA and IgM), T cell counts and Beta-2 microglobulin (b2M). Correlative studies will be conducted to understand changes in the immunological and cytokine/chemokine pathways in CLL in response to ruxolitinib. Correlative studies will only be performed at MDACC at visits: Day 1 (pre-dose), Month 3 \pm 7 days, and Month 6 \pm 2 mos., or as requested by the PI for specific patients with unusual response or unusual clinical presentation. Complete blood counts should be monitored every 2-4 weeks at MDACC or by the patients local physician until counts are stabilized. After month 8 \pm 2 mos., the patient is required to have a physical exam, hematology and chemistry every 2 months \pm 2 mos, every other visit may be conducted by the patient's local physician if more convenient for the patient. A bone marrow aspiration and biopsy and whole body CT scan will be completed at screening (-15-1 day) and at 6 months \pm 2 months of treatments (as per standard of care for CLL/SLL) will be performed at MDACC. We will use the CLL/SLL module of the MD Anderson Symptom Inventory and Brief Fatigue Inventory (measuring symptoms "at their worst") of common symptoms associated with CLL/SLL at every visit to MDACC.

8.1 Outside Physician Participation during Treatment

1. MDACC Physician communication with the outside physician is required prior to the patient returning to the local physician. This will be documented in the patient record
2. A letter to the local physician outlining the patient's participation in a clinical trial will request local physician agreement to supervise the patient's care (Appendix H)
3. Protocol required evaluations outside MDACC will be documented by telephone, fax or e-mail. Fax and/or e-mail will be dated and signed by the MDACC physician, indicating that they have reviewed it.
4. Changes in drug dose and/or schedule must be discussed with and approved by the MDACC physician investigator, or their representative prior to initiation, and will be documented in the patient record.

5. A copy of the informed consent, protocol abstract, treatment schema and evaluation during treatment will be provided to the local physician.
6. Documentation to be provided by the local physician will include drug administration records, progress notes, reports of protocol required laboratory and diagnostic studies and documentation of any hospitalizations.
7. The home physician will be requested to report to the MDACC physician investigator all life threatening events within 24 hours of documented occurrence.
8. Patient will have a physical exam every 1-2 months.

Patients are allowed to have hematology and biochemistry tests performed in outside laboratory facilities. Laboratory results will be obtained by the research staff assigned to this study. The PI or treating physician listed on the delegation of authority log will review outside labs and determined the clinical significance of these labs. The physician will sign and date the outside lab result.

Follow-ups and disease burden assessments will only be performed by the MD Anderson Cancer Center team. Patients must be followed for SAE/AEs until at least 30 days after the last dose of study drug. SAE/AE will be assessed on their next visit to the leukemia clinic at MDACC. Participant will be removed from the protocol study after the 30-day post-treatment visit/assessment.

All protocol specific data will be entered into PDMS/CORe.

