1.2 Secondary Objective

To evaluate the time to next treatment in high-risk CLL/SLL who do not require anti-neoplastic therapy according to the IWCLL 2008 recommendations.

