2.1.2 Previously untreated patients with high-risk CLL/SLL

[figure not shown]
The clinical course of patients with CLL/SLL is diverse; some patients have indolent disease, never needing treatment, whereas others have aggressive disease requiring early intervention. We currently use clinical criteria to initiate therapy. However several investigators suggested that early intervention in patients with high-risk disease might be beneficial. To determine which patients are at high risk of disease progression, a multivariable analysis was performed to identify prognostic factors independently associated with time to first treatment for patients with CLL (Wierda et al., 2011). This multivariable model was used to develop a nomogram—a weighted tool to calculate 2- and 4-year probability of treatment and estimate median time to first treatment.

The factors independently associated with shorter time to first treatment included: **a.)** three involved lymph node sites, **b.)** increased size of cervical lymph nodes, **c.)** presence of 17p deletion or 11q deletion assessed by fluorescence in situ hybridization (FISH), increased serum lactate dehydrogenase (LDH), and unmutated IgHV (Wierda et al., 2011).

Given that ruxolitinib is well tolerated and efficiently alleviates the symptoms of patients with CLL/SLL and given that, similar to ibrutinib, treatment with ruxolitinib increased and then reduced the number of circulating lymphocytes, we sought to investigate the clinical benefits of ruxolitinib in patients with previously untreated high-risk CLL/SLL. In particular, we intend to study the effect of ruxolitinib on disease burden and determine whether treatment with ruxolitinib will delay the time to next treatment of previously untreated patients with high-risk CLL/SLL who are expected to require therapy for CLL/SLL within 4 years according to the above described nomogram (Wierda et al., 2011).

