3.1.1 Inclusion criteria

- 1) Subjects who are able to understand and sign an informed consent document.
- 2) Subjects 18 years of age or older.
- 3) Subjects must be diagnosed with CLL/SLL and do not meet the IWCLL criteria for treatment (Hallek et al., 2008).
- 4) Patients should be previously untreated or have only been treated with single agent ibrutinib therapy for a period of < 3 months and were deemed ibrutinib intolerant.
- 5) Patients whose expected time to CLL/SLL treatment, according to our nomogram (Figure 1), is four years of less.
- 6) Subjects with hemoglobin values at the screening visit equal to or greater than 12.0 g/dL.
- 7) Subjects with a platelet count of at least $100 \times 10^9/L$ at the screening visit.
- 8) Subjects with an absolute neutrophil count (ANC) of equal to or higher than $0.5 \times 10^9/L$ at the screening visit.

- 9) Subject who are willing to undergo a bone marrow aspiration and biopsy and CT scan for disease burden assessment.
- 10) Patient who are capable to return to MDACC for follow-up.
- 11) Subjects with an Eastern Cooperative Oncology Group (ECOG) performance status of 0, 1 or 2.
- 12) Patient must be capable of swallowing the Ruxolotinib capsules (tablets).

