4.4 Patient Assessments

Patients will be presented with the informed consent at screening. They will fill out the Brief Fatigue Inventory (BFI) and the MD Anderson Symptom Inventory (MDSI) at each visit to MDA starting on Day 1. Patients will be seen at MDA during the screening period (-15-1 day), Day 1, Day 15 \pm 7 days, Month 2 \pm 7 days, Month 3 \pm 7 days, Month 6 \pm 2 months and Month 8 \pm 2 months, 10, 12, and so on. Every clinic visit to MDACC will include a routine physical examination, Brief Fatigue Inventory (BFI) and MD Anderson Symptom Inventory (MDSI) questionnaires and standard laboratory tests including CBC with differential and, plts, chemistries to include creatinine and ALT, Immunoglobulin levels (IgG, IgA and IgM), T cell counts and Beta-2 microglobulin (b2M).

If you can become pregnant, blood (about 1 teaspoon) and/or urine will be collected for a pregnancy test.

Correlative studies will be conducted to understand changes in the immunological and cytokine/chemokine pathways in CLL in response to ruxolitinib. Correlative studies will only be performed at MDACC visits: Day 1 (pre-dose), Month 3 \pm 7 days, and Month 6 \pm 2 mos. or as requested by the PI for specific patients with unusual response or unusual clinical presentation. Complete blood counts should be monitored every 2-4 weeks at MDACC or by the patient's local physician until counts are stabilized.

After month 8 \pm 2 mos the patient is required to have a physical exam, hematology and chemistry every 2 months \pm 2 mos. (Month 10, 12, and so on.) Every other visit may be conducted by the patient's local physician if more convenient for the patient.

Follow-Up

About 30 days after your last dose of ruxolitinib, blood (about 2 teaspoons) will be drawn for routine tests.

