9.1 Disease Response Criteria

Clinical response will be assessed based on physical examination, CBC, a bone marrow aspiration, a whole body CT scan to be done at screening and 6 ± 2 months in accordance with the IWCLL guidelines (Hallek et al., 2008) as outlined in Table 8. If a 20% reduction in tumor burden is observed at 6 ± 2 months, Treatment will be continued as long as a CR, PR or at least a 20% reduction in tumor mass is achieved and sustained.

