10.0 CRITERIA FOR REMOVAL FROM THE STUDY

Patients will be removed from the study for the following reasons:

1. Pattern of noncompliance.
2. Toxicity (grade 3 or 4) inducing clinical symptoms necessitating red blood cell or platelet transfusions and not alleviated after dose adjustment.
3. Disease progression that require another therapeutic intervention (an increase in peripheral blood lymphocyte count is expected. If needed anti-CD20 antibody treatment (Rituximab or Ofatumumab) or leukopheresis are allowed).
4. Lack of response (a reduction of 20% of tumor mass or PR) at 6 ± 2 months.
5. Unexpected events (medical or other) that would prevent the patient from staying on study.
6. Patient's or physician's choice. Compliance will be assessed by the P.I. based on the drug accountability documented by the site staff and monitored by the designee. The objective is 100% compliance and the P.I. and his staff will evaluate compliance at each visit, and take appropriate steps to optimize compliance. For the purpose of subgroup analyses, subjects with at least 80% compliance over the total duration of dosing from the first day of dosing to the analysis of the study will be considered to be compliant.

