11.0 STATISTICAL CONSIDERATIONS

The study will be conducted at MDACC only. The primary endpoint will assess the clinical response (CR, PR, and a 20% reduction in tumor mass as assessed by a body scan and bone marrow aspiration/biopsy) at 6 ± 2 months after initiation of therapy.

We will incorporate an informal futility analysis when half of the total patients have reached 6 ± 2 months after initiation to assess whether the average change in the tumor mass score is less than zero (calculated as the score at enrollment minus the score at six months). If the average at this time is less than zero, the trial will be stopped early.

Because no treatment is the standard of care for these patients, we will routinely analyze the outcome of our Ruxolitinib-treated patients at a 6 \pm 2 month interval and compare their clinical outcome to that of patient who elected to receive no treatment.

Table 9 shows the probability of stopping early under several different scenarios, as well as how the overall power is for the primary analysis is affected by early stopping. The operating characteristics were produced in R version 2.13.0 by simulating 5000 trials with 17 patients at the interim and 34 patients at the end of the trial, accounting for a 15% drop out rate. The simulations stop early if the average change at 6 months is less than zero, and formally tests whether the change is not equal to zero at the final analysis using a paired *t*-test.

Table 9. Operating characteristics

True tumor burden difference (baseline score minus score at 6 months)	True SD of the Difference	Prob(Stop Early)	Power for Final Analysis
-1	2	0.9818	0.0026
0	2	0.5068	0.0218
1	2	0.0202	0.8064
2	2	0.0000	0.9998
-1	4	0.8398	0.0014
0	4	0.4958	0.0274
1	4	0.1584	0.2876
2	4	0.0198	0.8074

For primary analysis, the paired *t* test will be used to evaluate the changes of tumor burden from baseline to 6 \pm 2 months after initiation of therapy. Response rate will be estimated with 95% confidence interval. Patients who drop out early will be counted as non-responders. The Kaplan-Meier method will be used to estimate time to next treatment, and will compared to our historical data (Wierda et al., 2011) using Cox proportional hazards model, adjusting for effects of covariates. If necessary and applicable, appropriate methods such as propensity score matching will be used to match the patients of this study with the historical data to reduce comparison bias.

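### Section 8.1 ends participation 30 days after ruxolitinib stops, with no later collection of next-treatment dates and no censoring rule; if followed as written, time to next treatment loses events and probably favours ruxolitinib

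*Combined protocol and SAP*

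**What the plan says.** Section 1.2 gives one secondary objective: "To evaluate the time to next treatment in high-risk CLL/SLL who do not require anti-neoplastic therapy". Section 2.1.2 states the aim more strongly, as wanting to "determine whether treatment with ruxolitinib will delay the time to next treatment of previously untreated patients with high-risk CLL/SLL". Section 11.0 gives the analysis: "The Kaplan-Meier method will be used to estimate time to next treatment, and will compared to our historical data", by a Cox model with covariate adjustment and possibly propensity matching. It gives no censoring rule for this endpoint. Its rule that early drop-outs count as non-responders concerns the response rate.

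Several provisions decide when a patient stops drug and how long the patient is then followed:

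- Section 10, item 4, lists as a reason for removal: "Lack of response (a reduction of 20% of tumor mass or PR) at 6 ± 2 months". Item 3 separately covers progression that requires another therapy, so item 4 reaches patients who have not yet needed one.
- Section 9.1 adds that "Treatment will be continued as long as a CR, PR or at least a 20% reduction in tumor mass is achieved and sustained".
- Section 4.4, under Follow-Up, describes one post-treatment procedure: "About 30 days after your last dose of ruxolitinib, blood (about 2 teaspoons) will be drawn for routine tests".
- Section 8.1 then closes participation: "Participant will be removed from the protocol study after the 30-day post-treatment visit/assessment".

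Section 12.2 keeps one channel open after 30 days, for serious adverse events related to treatment. It does not cover next therapy.

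**The concern.** Kaplan-Meier and Cox both assume that patients who leave the risk set have the same future hazard as comparable patients who stay. Here a main reason for leaving is failure to reach a 20% tumour reduction or PR. Those patients are plausibly closer to needing treatment than patients whose disease has shrunk. If their follow-up ends a month after the last dose, the later part of the curve rests mostly on responders, while the historical cohort keeps patients of every kind. The treatment-free curve would then sit too high and the hazard ratio too low even if the drug did nothing. Adjustment for baseline covariates removes only the part of this that baseline factors explain, because response is observed after baseline.

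At stake is the one analysis that speaks to whether ruxolitinib delays treatment. The primary endpoint is read at 6 ± 2 months, before this exit rule bites, so it and Table 9 are not affected.

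**Working it through.** **The plan's own figures.** The plan states no power, event count or sample size for time to next treatment, so there is no figure of its own to reproduce. Table 9 concerns the primary paired t-test and does reproduce (difference 1, SD 2: simulated power 0.807 against the stated 0.8064). Its 34 patients with 15% drop-out give 34/0.85 = 40, the maximum in Tables 10 and 11.

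**Inputs from the plan.** Removal for non-response at 6 ± 2 months (Section 10). Exit about one month after the last dose (Section 8.1), hence month 7, with a range of 5 to 9. Eligibility: "Patients whose expected time to CLL/SLL treatment, according to our nomogram (Figure 1), is four years of less" (Section 3.1.1). Treatment for up to 3 years (Section 4.3), hence month 36 as the reading point.

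**Assumed inputs, not in the plan.** Exponential times. Share of non-responders q = 0.3, 0.5, 0.7. Overall median M = 24, 36, 48 months. Non-responder hazard k = 1, 2 or 4 times the responder hazard h.

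**Formulas.** Only item 4 exits are modelled.

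- Overall curve: S(t) = q·exp(−kht) + (1−q)·exp(−ht), with h solved so that S(M) = 0.5.
- Full follow-up at month 36: S(36).
- As written: S(7) × exp(−29h), because only responders remain at risk after month 7.
- Expected events by month 36 in 40 patients: 40 × [1 − S(36)] with full follow-up; 40 × {q[1 − exp(−7kh)] + (1−q)[1 − exp(−36h)]} as written.

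**Middle case (q = 0.5, M = 36, k = 2).** With x = exp(−36h), 0.5x² + 0.5x = 0.5 gives x = 0.618 and h = 0.01337 per month.

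- S(7) = 0.5 × 0.829 + 0.5 × 0.911 = 0.870.
- As written: 0.870 × exp(−29 × 0.01337) = 0.870 × 0.679 = 0.590, against 0.500 with full follow-up. Exit at month 5 gives 0.598; at month 9, 0.583.
- Events: 40 × 0.500 = 20.0 with full follow-up; 40 × (0.5 × 0.171 + 0.5 × 0.382) = 11.1 as written.

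**Whole grid.**

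| Hazard ratio k | Month-36 estimate too high by | Events by month 36 lost |
|---|---|---|
| 1 | 0 points | 22% to 53% |
| 2 | 5.2 to 13.1 points | about 25% to 60% |
| 4 | 8.4 to 23.0 points | about 25% to 65% |

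The smallest loss is 25.9 to 20.3 events (M = 24, q = 0.3, k = 1); the largest is 16.5 to 5.7 (M = 48, q = 0.7, k = 4).

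**Cross-checks.** A separate simulation of 400,000 patients per scenario, with the remaining patients leaving at month 37, gives 0.591 against 0.500 in the middle case and an excess of about 3 to 19 points for k between 1.5 and 3. In a simulated unadjusted Cox comparison with a historical cohort of the same mix and no drug effect, the hazard ratio is 1.00 at k = 1, 0.80 in the middle case, 0.77 to 0.88 over the grid at k = 2, and 0.61 to 0.82 at k = 4.

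**The case against.** **The plan does not say these patients are censored.** A reader might infer that Section 11.0 prescribes censoring at exit. It does not; it is silent. The Section 8.1 sentence closes a paragraph on adverse-event follow-up and could mean only that protocol procedures end. This is a single-centre study, and later treatment may appear in the centre's charts. The consent form and appendices are not in the available text and might provide for longer follow-up. All of this stands, so the censoring is a consequence of following the text, not a stated rule. But no visible section plans chart capture. Local physicians may share the care during treatment, so unplanned capture could be incomplete.

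**The direction is not proven.** No document gives a non-responder hazard, and at equal hazards the bias is zero. Exits for toxicity, noncompliance or choice could act either way. Patients removed because progression requires therapy can be counted as events. The Cox figures also suppose that 30-70% of patients meet the response criterion without any drug effect and carry lower risk, which nothing in the plan supports. This too stands; it is why the size is illustrative.

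**The bias is modest against the noise.** In the middle case the month-36 estimate has a sampling SD of about 0.10 with 40 patients (4,000 simulated trials), so 9 points is about one SD. With 11 events the standard error of the log hazard ratio is at least 1/√11 = 0.30, and a ratio of 0.80 has a 95% interval of about 0.44 to 1.45. That limits what this secondary endpoint can show, but it is no reason to accept an avoidable systematic error and lose events as well.

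**Loss of response in responders.** From Section 9.1 a reader might infer a much larger distortion, with every responder censored at loss of response. CT and marrow are scheduled only at screening and 6 ± 2 months, so complete detection is not realistic. No weight is put on that scenario.

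**Conclusion.** The concern holds in a limited form. Section 8.1 ends participation after the 30-day visit, and the available text neither collects later next-treatment dates nor defines censoring for the only secondary objective. Applied as written, it would in effect censor patients who stop before needing therapy, chiefly those removed under Section 10, item 4.

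That censoring favours ruxolitinib if non-responders are nearer to treatment than patients still on drug: likely, not certain. On the assumptions listed, the month-36 treatment-free probability is overstated by 0 points at equal hazards, 5-13 at twice the hazard and 8-23 at four times, and 22-65% of events by month 36 are lost. Event loss occurs even where bias does not. A reader might go further and conclude that the comparison is bound to be biased by a known amount; the documents do not support that. The point is worth correcting because the remedy is cheap, but it does not threaten the primary analysis.

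**What to change.** 1. Section 8.1, replace the quoted sentence with: *Adverse event collection ends at the 30-day post-treatment visit (except late related SAEs, Section 12.2). Unless consent is withdrawn, the date and type of next CLL/SLL treatment and vital status are collected by phone or chart about every 6 months in every patient who stops ruxolitinib for any reason, to a common cutoff of month 36 from enrolment.*
2. Section 10: change the lead-in to *removed from study treatment*, so that it agrees with item 1.
3. Section 11.0, add: *Patients without a next treatment are censored at the last date known to be free of next treatment (study visit, phone or chart, on or off ruxolitinib), and all patients, on or off drug, are administratively censored at month 36.*
4. State whether the anti-CD20 antibody or leukapheresis allowed in Section 10 counts as next treatment.

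The cutoff must be common to all. Section 4.3 allows drug beyond 3 years; if follow-up after stopping ended at month 36 while on-drug patients continued, a smaller version of the bias would return. In the middle case this gives 0.500 × exp(−12 × 0.01337) = 0.426 at month 48 against a true 0.402.

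Cost: contacts at months 6, 12, 18, 24, 30 and 36, so at most 6 per patient and 6 × 40 = 240 in all, plus any consent wording needed. No extra patients, visits, scans or marrow samples.
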